Annex 1: The dataset

Annex 1 defines the data elements to be used for estimating brand-specific VE in a population based cohort study using secondary data from pre-existing databases. The minimum dataset is marked with an asterisk(*), but preferably the most important covariates to adjust for will be included. According to these data elements, the analysis database will be developed to include the defined outcome events by person months vaccinated, (partially vaccinated) and unvaccinated, considering the events leading to right-censoring, and the covariates needed for adjustment or stratification.

The database may alternatively be structured for aggregated data, initially based on these data elements.

Instructions for harmonisation of the variables and the structure of analysis database will be provided in the generic study site level Statistical Analysis Plan (SAP), Annex 2. Season-specific updates in Annex 2 will be implemented to Annex 1, if needed.

DRIVE – The dataset for estimating VE in a population based cohort study using secondary data from pre-existing databases. The minimum data set is marked with an asterisk(*)�.

	Variable	Description	Format	Values and coding	Example
General	idcountry*	Country code defined in ISO 3166-1 alpha-2	2 letters text		Finland
	id*	Patient or aggregate identification number	Unique integer		12345678
	cohort*	Cohort name	Text		THL
	region*	Region name	Text		Pirkanmaa
	dataset*	Data set name	text		Elderly
	sex*	Sex	Numeric (Binary)	0=Female 1=Male	0
	dob* (alternatively age)	Date of birth or age at the start of the follow-up (children: months; adults:years)	dd/mm/yyyy	Date between the date of birth of the oldest and youngest study subject	01/01/1960

The follow-up	startdate*	Date of the start of the study period	dd/mm/yyyy	Date within the study period	30/12/2017
	enddate*	Date of the end of the study period ^a	dd/mm/yyyy	Date within the study period	30/12/2017
	middledate	Date separating the early and the middle epidemic season	dd/mm/yyyy	Date within the study period	30/12/2017
	latedate	Date separating the middle and the end epidemic season	dd/mm/yyyy	Date within the study period	30/12/2017
	death*	Died during the follow-up	Numeric (Binary)	0=No 1=Yes	1
	deathdate*	Date of death ^a	dd/mm/yyyy	Date within the study period	30/12/2017
	moved(*)	Moved out of the cohort catchment area during the follow-up	Numeric (Binary)	0=No 1=Yes	1
	movedate(*)	date of moving out of the catchment area of the cohort ^a	dd/mm/yyyy	Date within the study period	30/12/2017
	Outcome/ right-censoring dates	infl*	Any positive influenza test during the follow-up	Numeric (Binary)	0=No 1=Yes
		infldate*	Date of positive influenza test ^b	dd/mm/yyyy	Date within the study period
		inflA*	Any positive influenza A test during the follow-up	Numeric (Binary)	0=No 1=Yes 9999=No information

	inflAdate*	Date of positive influenza A test ^b	dd/mm/yyyy	Date within the study period (no information =99/99/9999)	30/12/2017
	inflH1N1	Any positive influenza A(H1N1) test during the follow-up	Numeric (Binary)	0=No 1=Yes 9999=No information	1
	inflH1N1date	Date of positive influenza A(H1N1) test ^b	dd/mm/yyyy	Date within the study period (no information =99/99/9999)	30/12/2017
	inflH3N2	Any positive influenza A(H3N2) test during the follow-up	Numeric (Binary)	0=No 1=Yes 9999=No information	1
	inflH3N2date	Date of positive influenza A(H3N2) test ^b	dd/mm/yyyy	Date within the study period (no information =99/99/9999)	30/12/2017
	inflB*	Any positive influenza B test during the follow-up	Numeric (Binary)	0=No 1=Yes 9999=No information	1
	inflBdate*	Date of positive influenza B test ^b	dd/mm/yyyy	Date within the study period (no information =99/99/9999)	30/12/2017
	inflYamagata	Any positive influenza B/Yamagata test during the follow-up	Numeric (Binary)	0=No 1=Yes 9999=No information	1

	inflYamagatadate	Date of positive influenza B/Yamagata test ^b	dd/mm/yyyy	Date within the study period (no information =99/99/9999)	30/12/2017
	inflVictoria	Any positive influenza B/Victoria test during the follow-up	Numeric (Binary)	0=No 1=Yes 9999=No information	1
	inflVictoriadate	Date of positive influenza B/Victoria test ^b	dd/mm/yyyy	Date within the study period (no information =99/99/9999)	30/12/2017
	outcomeXdate	Date of defined time of outcome X ^c	dd/mm/yyyy	Date within the study period	30/12/2017
Exposure/ right-censoring dates	inflvac	Vaccination at least once with any influenza vaccine during the follow-up	Numeric (Binary)	0=No 1=Yes	1
	inflvacdate*	First date of any influenza vaccination ^d	dd/mm/yyyy	Date within the study period	30/12/2017
	inflvac2	Vaccinated twice with any influenza vaccine during the follow-up	Numeric (Binary)	0=No 1=Yes	1
	inflvacdate2	Second date of any influenza vaccination ^e	dd/mm/yyyy	Date within the study period	30/12/2017
	brandX	Vaccination at least once with brand X during the follow-up	Numeric (Binary)	0=No 1=Yes 9999=No information	1

	brandXdate1*	First date of the influenza vaccination brand X ^d	dd/mm/yyyy	Date within the study period (no information =99/99/9999)	30/12/2017
	brabdX2	Vaccinated twice with brand X during the follow-up	Numeric (Binary)	0=No 1=Yes 9999=No information	1
	brandXdate2	Second date of the influenza vaccination brand X ^e	dd/mm/yyyy	Date within the study period (no information =99/99/9999)	30/12/2017
	vactypeX	Vaccination at least once with type X vaccine during the follow-up	Numeric (Binary)	0=No 1=Yes 9999=No information	1
	vactypeXdate1*	First date of the influenza vaccination type X ^d	dd/mm/yyyy	Date within the study period (no information =99/99/9999)	30/12/2017
	vactypeX2	Vaccinated twice with type X during the follow-up	Numeric (Binary)	0=No 1=Yes 9999=No information	1
	vactypeXdate2	Second date of the influenza vaccination brand X ^e	dd/mm/yyyy	Date within the study period (no information =99/99/9999)	30/12/2017
Potential confounders/effectors	Other vaccinations				

ct modifiers	seasvacn1	Received influenza vaccination in previous season (season n – 1)	Numeric (Categorical)	0=No 1=Yes, full vaccination 2=Yes, partial vaccination ^f 9999=No information	1
	seasvacn2	Received influenza vaccination in season n – 2	Numeric (Categorical)	0=No 1=Yes, full vaccination 2=Yes, partial vaccination ^f 9999=No information	1
	pneumovacdate	Date of pneumococcal vaccination during the study period	dd/mm/yyyy	Date within the study period	21/11/2017
	prevpneumovac	Received pneumococcal vaccine before study period started	Numeric (Categorical)	0=No 1=Yes 9999=No information	
Chronic conditions					
	liverdis	Chronic liver disease	Numeric (Categorical)	0=No 1=Yes 9999=No information	0
	diabetes	Diabetes	Numeric (Categorical)	0=No 1=Yes 9999=No information	0

heardis	Heart or cardiovascular disease	Numeric (Categorical)	0=No 1=Yes 9999=No information	1
cancer	Cancer	Numeric (Categorical)	0=No 1=Yes 9999=No information	0
immuno	Immunodeficiency or organ transplant	Numeric (Categorical)	0=No 1=Yes 9999=No information	0
autoimmun	Autoimmune disease	Numeric (Categorical)	0=No 1=Yes 9999=No information	0
lungdis	Lung disease	Numeric (Categorical)	0=No 1=Yes 9999=No information	1
anemia	Anemia	Numeric (Categorical)	0=No 1=Yes 9999=No information	0
rendisease	Renal disease	Numeric (Categorical)	0=No 1=Yes 9999=No information	0
dement	Dementia	Numeric (Categorical)	0=No 1=Yes 9999=No information	0

stroke	History of stroke	Numeric (Categorical)	0=No 1=Yes 9999=No information	0
rheumat	Rheumatologic diseases	Numeric (Categorical)	0=No 1=Yes 9999=No information	0
obesity	Obesity	Numeric (Categorical)	0=No 1=Yes 9999=No information	0
chronic1	At least one chronic disease	Numeric (Binary)	0=No 1=Yes 9999=No information	1
chronic5	At least 5 chronic diseases	Numeric (Binary)	0=No 1=Yes 9999=No information	1
Pregnancy and perinatal/congenital risk factors (in children)				
pregnancy	Pregnancy at start of the study period	Numeric (Categorical)	0=No 1=Yes 9999=Not applicable	0
childrisk	Any perinatal or congenital risk factor in children	Numeric (Categorical)	0=No 1=Yes 9999=No information	0

Health care utilisation and propensity score				
nhosp	Number of hospitalisations 12 months prior to the study period	Numeric	≥0 or 9999=No information	2
nphcvisit	Number of outpatient primary health care visits to physician 12 months prior to the study period	Numeric	≥0 or 9999=No information	5
adherence	Adherence in the childhood vaccination program (in children)	Numeric (Categorical)	0=No 1=Low 2= Moderate 3= Complete 9999=No information	3
propensity score	Quintiles of the probability to be vaccinated according to background factors	Numeric	1-5	4
Life style, medications, social and functional status and miscellaneous				
siblings	(In children) Number of siblings living	Numeric	≥0 or 9999=No information	2
bmi	Body Mass Index	Numeric	10 to 55 or 9999=No information	22.4
smoking	Smoking status (parental smoking in children)	Numeric (Categorical)	0=Non-smoker 1=Ex-smoker 2=Smoker 9999=No information	0

dependency	Patient has contract to regular home care or difficulty in at least one category of daily living ^g	Numeric (Categorical)	0=No 1=Yes 9999=Not applicable	0
inst	Institutionalized	Numeric (Categorical)	0=No 1=Yes 9999=No information	0
contra	Contraindication for influenza vaccination	Numeric (Categorical)	0=No 1=Yes 9999=No information	0
sosstatus	Socio-economic status or applicable proxy	Numeric (Categorical)	1=low 2=medium 3= high 9999=No information	2
antiviral	Antiviral use during follow-up	Numeric (Categorical)	0=No 1=Yes 9999=No information	1
statin	Statin use during follow-up	Numeric (Categorical)	0=No 1=Yes 9999=No information	1

^adate of an event leading to right-censoring/end of follow-up of the analysis^bone of these dates is the analysis-specific outcome date and the others are dates for events leading to right-censoring.^crefers either to non-specific outcomes (e.g. visit, hospitalisation, start of a disease episode) or onset defined as proxy for start of the specific outcome disease. Outcome dates will be defined for all outcomes used.^done of these dates is the analysis-specific exposure date and the others are analysis-specific dates for events leading to right-censoring. There must be as many exposure dates as there are vaccine brands/types available in the database^efor children aged <9 years who have not been fully vaccinated before the current season (i.e. received at least two doses of injectable vaccine or one dose of LAIV).^fone dose of injectable vaccine in children aged <9 years who had not been fully vaccinated (see^e) before the season in question (season n-1 or season n-2)^gbathing, dressing, eating, going to the toilet, stairs, walk, wheelchair user

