To measure seasonal IVE against medically attended laboratory-confirmed influenza, by vaccine brand, then by vaccine type (e.g. by antigen preparation strategy, number of virus strains, adjuvant; see section *Exposure*), then by overall influenza vaccination.

Secondary objectives

To estimate IVE (brand-specific, type specific and total, if possible) against laboratory-confirmed influenza by:

- age group (children, young adults and elderly; the age groups will be further defined in the generic study site level SAP)
- influenza virus type (A, B) and/or subtype (A/H1N1, A/H3N2) and lineage (B/Victoria, B/Yamagata)
- severity/level of health care required (primary health care, hospitalisation)
- risk groups / target groups for vaccination, e.g
 - pregnant women
 - healthcare workers
 - any chronic condition (see Annex 1 and Annex 2)
 - specific chronic conditions (see Annex 1 and Annex 2)
- time since vaccination
- time window in the epidemic season (early, middle, end)(see section Study period)
- previous influenza vaccinations (one or preferably more previous seasons)

To estimate IVE (brand-specific, type specific and total, if possible) against non-specific outcomes with public health relevance, e.g.

- suspected or diagnosed influenza requiring medical attention (primary care and/or hospitalisation)

- respiratory infection, pneumonia or other respiratory conditions requiring hospitalisation, intensive unit care, or leading to death other non-specific outcomes such as cardiovascular events or deterioration of chronic conditions

To estimate brand-specific, type specific or total IVE against laboratory confirmed influenza and/or unspecific outcomes across several seasons, considering the local circulation of the strains and clades detected by the virus surveillance systems, if possible

The details of the analyses will be prescribed in the generic study site level SAP, updated annually according to the characteristics and structure of data available at the participating study sites

Methods

Study design

In each participating study site, a cohort study using secondary data from existing databases or health care registers (see section *Cohort of interest*). To reach appropriate sample size for assessing brand-specific VE, the data from individual studies will be pooled.

Study setting

The population-based study setting is defined by each study site, based on the available data.

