- *Each study site to describe the source population and definition of the study cohort Each study site to specify the target groups for which influenza vaccination is recommended, which vaccines are used in the database catchment area, and how the choice of vaccine brand happens*

Study period

The study follow-up will start before the seasonal influenza vaccine is available and before the influenza virus circulation begins in the country/region, to ensure that all vaccinations and all outcomes in the defined cohort are captured. If only aggregated data will be collected that does not allow the shortening of the study subjects' follow-up as part of the statistical analysis, the follow-up may be restricted to the time the vaccine first becomes available or the virus circulation starts, whichever occurs first. The study period will finish at the end of the influenza season.

- *Each study site to specify the study period: the definition of the beginning and end of the study period*
- *Each study site to specify the early, middle and end of the influenza epidemic at the study site according to the information provided by the local influenza surveillance system.*

For the pooled analysis, a harmonised minimum period will be defined (e.g. from week 40 till week 20), but if needed, it will be extended to fully cover the vaccination campaign and the epidemic in each study site. Definition of shorter time periods (e.g. early, middle and end season) will be developed to take into account differences in influenza activity over time and probable development of immunity in unvaccinated population through encounters with the circulating viruses

For addressing the secondary objective of estimating influenza vaccine effectiveness over several seasons, multiple study periods will be combined. If possible, the information from the local surveillance systems of major circulating strains in the study regions will be considered in the analysis. The details of the analysis will be described in the generic study site level SAP.

Study population and follow-up

Cohort of interest

The study cohort comprises the characterised by place of residence, or catchment population of a health care service providing the relevant information for the analyses. The databases may also be characterised by or restricted to e.g. age, or medical, physiological or occupational conditions (e.g. pregnancy, health care workers, other risk/target groups).

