The study cohort is defined at a fixed time point at the start of the study period. The study subjects will be prospectively followed in time for having a record for vaccination and for occurrence of the defined outcome event. The subjects will leave the follow-up at dynamic time points, either at occurrence of the defined outcome, or e.g. death, but latest at the end of the study period (see section ‘Individual follow-up’). If the data sources are available without remarkable delay, the study cohort may be defined and followed concurrently [14], which may allow providing the VE estimate almost in real-time. If there is delay in availability of the data sources or resources, the same cohort and follow-up can be constructed afterwards, in which case the follow-up is named non-concurrently. The data (the cohort population, vaccination, occurrence of the outcome and confounders/effect modifiers) are derived from pre-existing registers and databases, which ideally can be linked on individual bases by an unique identifier, or as aggregates allowing estimation of VE (see section Sources of information)

- *Each study site to specify and describe the study population, the cohort of interest and the follow-up.*

Outcome

Specific outcome: laboratory-confirmed influenza

The specific outcome, laboratory-confirmed influenza (LCI), will be detected through one of the following laboratory tests, according to the practices of sites providing the primary data into the database(s) used in the study: reverse transcription-polymerase chain reaction, viral culture, and immunofluorescence or rapid influenza diagnostic tests based on antigen detection, the positive or all results of which are transferred to the database used in the study. Each positive test result is to be classified by influenza type (A and B) and preferably also subtype (A/H1N1, A/H3N2) and lineage (B/Victoria, and B/Yamagata).

Usually the sampling will be driven by the local medical practices and/or the decision by the clinician. It may also be possible that sampling has followed a pre-defined protocol, if the cohort database is primarily established for study purposes.

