- Population and demographic registers
- Registers of catchment of medical care or assurance
- Registers of vaccinations
- Registers of GP/primary health care visits and diagnoses
- Registers of outpatient and inpatient visits and diagnoses in secondary health care
- Registers for reimbursement (medicines, vaccines, medical treatments/measures for outcome or chronic diseases)

- Registers for prescriptions and those showing evidence of pharmacy delivery (medicines, vaccines)
 - Registers for diagnostic microbiological test results
 - Causes of death registers
 - Medical birth registers (timing of pregnancy, perinatal and congenital problems)
 - Cancer registers
 - Registers for congenital malformations
 - Registers of housing, nursing and other social services
 - Registers established for study purposes
- *Each study site to describe the databases (contents, origin) that will be used in the study for assessing information of the exposure, defined outcomes and data of potential confounders and effect modifiers will be derived from (see sections Outcome, Exposure, and Potential confounders and effect modifiers).*

Sample size considerations

This section gives sample size considerations and formulates recommendations. These recommendations are meant to support the design of the cohort studies on IVE. Obtaining a minimum sample size is not a requirement for study participation. Details on the sample size calculations based on the minimal detectable VE as well as precision are given in Annex 3.

DRIVE recommends cohort studies based on 5000 subjects or more. However, studies with smaller sample sizes might still contribute to the power of the pooled analyses, provided that the study site is able to optimally harmonise its protocol with the other study sites to minimize the between-study heterogeneity. In case VE estimates with unacceptable large CIs are obtained, it might be considered to not report these estimates.

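### Annex 1 records pregnancy only as a yes/no at study start, so current status is increasingly misclassified as the season proceeds: roughly 25% to 58%, depending on when the epidemic falls.

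*Combined protocol and SAP*

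**What the plan says.** The only pregnancy variable in Annex 1 (The dataset) is "Pregnancy at start of the study period". It is coded no, yes or not applicable, and there is no start date, end date or field for pregnancy arising during follow-up.

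The variable has two possible uses. Secondary objectives list "pregnant women" among the risk and target groups for separate VE estimates. Potential confounders and effect modifiers lists pregnancy, but without the asterisk that marks the minimum set for pooling; only age and sex carry it.

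On timing, Study period states: "The study follow-up will start before the seasonal influenza vaccine is available and before the influenza virus circulation begins in the country/region". A later start, at vaccine availability or onset of circulation (whichever comes first), is allowed only for certain aggregated data. The follow-up section adds: "The study cohort is defined at a fixed time point at the start of the study period". The example window for pooling is given as follows: "a harmonised minimum period will be defined (e.g. from week 40 till week 20"). Epidemic timing is left open: "Each study site to specify the early, middle and end of the influenza epidemic at the study site".

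Sources of information includes this entry: "Medical birth registers (timing of pregnancy, perinatal and congenital problems"). The documents thus name a source that could date pregnancy, but Annex 1 does not carry those dates.

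**The concern.** Pregnancy lasts about as long as the study window, so a status fixed at the start goes out of date during follow-up. The plan places that start ahead of both exposure and outcome. Two errors follow: delivered women remain in the pregnant group, and newly pregnant women are counted outside it.

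For the subgroup, the estimate describes women pregnant around the start of the season rather than women pregnant when at risk of influenza. Each site sets its own study period, so the lag between flag and epidemic differs by site and the pooled subgroup is not one population. The error also grows with time, which affects any early, middle and late comparison within this subgroup.

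For adjustment, a pregnancy that begins after the start but before vaccination precedes the exposure. Because pregnant women are a target group, it may prompt vaccination. A start-of-study flag cannot capture it, nor can a propensity score built on baseline information.

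**Working it through.** The documents state no figure for pregnancy turnover, so there is nothing to reproduce. The following is a simple turnover model.

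**Inputs from the documents**
- Status is fixed at study start (Annex 1; the follow-up section).
- The example window runs from week 40 to week 20 (Study period), about 32.9 weeks.

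**Assumptions, not in the documents**
- Conception rate is constant, so gestational age at study start is uniform from 0 to L weeks.
- L is 38 or 40 weeks.
- Follow-up starts in week 40 of a 52-week year.
- Every pregnancy is detectable at the start.
- The epidemic falls somewhere from week 50 to week 10.

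**Formulas**
- Of women coded pregnant, those with gestation above L − t at the start have delivered by week t. Share delivered = t/L.
- Of women pregnant at week t, those who conceived in the last t weeks were not pregnant at the start. Share coded non-pregnant = t/L.

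**Results**

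| Calendar week | t (weeks since start) | t/40 | t/38 |
|---|---|---|---|
| 48 | 8 | 20.0% | 21.1% |
| 50 | 10 | 25.0% | 26.3% |
| 1 | 13 | 32.5% | 34.2% |
| 2 | 14 | 35.0% | 36.8% |
| 6 | 18 | 45.0% | 47.4% |
| 10 | 22 | 55.0% | 57.9% |

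- One third is reached at t = L/3: 38/3 = 12.7 weeks or 40/3 = 13.3 weeks, about week 1 to 2 for a week-40 start.
- The average over the example window is (32.9/2)/L = 41% (L = 40) or 43% (L = 38).

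**Earlier start.** Beginning 2 to 4 weeks before week 40 moves the week-1 share to between (13 + 2)/40 = 37.5% and (13 + 4)/38 = 44.7%.

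**Incomplete detection.** Suppose pregnancies under 6 weeks cannot be seen at the start. Then share delivered = t/(L − 6) and share missed = (t + 6)/L. At week 2 the share delivered is 14/34 = 41% to 14/32 = 44%. The share missed is 20/40 = 50% to 20/38 = 53%. The two shares are then no longer equal, and the missed share is the larger.

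**At vaccination.** Confounding depends on status around vaccination, not at the epidemic. If vaccination falls 4 to 8 weeks after the start (assumed, since the documents give no timing), t/L runs from 4/40 = 10% to 8/38 = 21%.

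**The case against.** The strongest reply is that the definition is not final. Sites must describe how each factor is identified, Annex 2 is still to be written, and it may update Annex 1. The subgroup in Secondary objectives is not expressly tied to the Annex 1 flag. Pregnancy is one of several subgroups to be studied where possible, and it is an optional covariate. This limits the seriousness of the point. It does not remove it: none of these provisions commits to dating pregnancy, and the one variable specified cannot later be turned into dates.

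A second reply is that baseline covariates are conventional. However, Annex 1 already carries in-season information for others: a date of pneumococcal vaccination, and antiviral and statin use during follow-up.

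A third reply concerns feasibility, and it stands in part. Aggregate data, and logistic regression on end-of-follow-up counts, cannot be split by time. The propensity score is defined on baseline information, so a time-dependent term does not fit inside it.

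A reader might also infer that more than a third of the group is bound to be misclassified by the epidemic. The documents do not support this. They give no epidemic timing, and in the model the share is only 20-32% in weeks 48 to 52. Nor is it safe to say that the two errors are always of similar size, since that needs full detection at the start.

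**Conclusion.** The point holds in conditional form. The Annex 1 field goes out of date by design. Under the stated assumptions, about 25-26% of the pregnant group has delivered at week 50, 35-37% at week 2 and 55-58% at week 10, and equal shares of currently pregnant women are coded non-pregnant. The share exceeds one third only from about 13 weeks after study start. Even the lower end is material for a named subgroup.

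It may be tempting to read these shares as a bias of known size in VE. The documents do not support that. The shift in the subgroup estimate depends on how far VE differs in and out of pregnancy, which they do not give; if VE and baseline risk were the same in both, this mixing would cause no shift. The confounding effect cannot be quantified either, and the relevant share at vaccination is smaller. Primary estimates are touched only where a site adjusts for this optional covariate.

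**What to change.** - **Dataset.** In Annex 1, and in Annex 2 when it is written, add optional pregnancy start and end dates, taken from the register sources already listed.
- **Sites with individual time-to-event or person-time data.** Split person-time by current pregnancy for the subgroup analysis. For adjustment, enter pregnancy as a time-dependent term in the outcome model, separate from the baseline propensity score.
- **Sites with only aggregate data, end-of-follow-up data or no dates.** Keep the baseline flag and report the subgroup explicitly as pregnant at study start.

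The cost is two optional fields and an extra time split; person-time is already divided by vaccination status. Apart from dating error, this would remove the misclassification for women whose dates are recorded. There are two downsides. Birth registers identify a pregnancy only after delivery, so sites working in near real time would need a later extract. Such registers may also miss pregnancies that do not end in a birth.
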